
Baseline analyses: For each baseline characteristic in the questionnaire (see attached document), we will examine the distribution and outliers. We will test whether baseline characteristics are balanced between intervention arms using parametric or non-parametric bivariate tests as appropriate. All tests will be conducted at $\alpha=0.05$.

Outcome analyses: Feasibility measures (described above) will be characterized with descriptive statistics (frequencies and proportions) using STATA statistical software. To assess the acceptability of the intervention and trial among study participants, [name] will conduct a series of exit interviews with HHAs and nurses in the trial, as well as with VNS Health staff. The effect of the intervention among HHAs will be assessed for **two primary outcomes:** 1) HF knowledge; 2) HF caregiving self-efficacy and **two secondary outcomes:** 1) intention to leave and 2) job satisfaction (See above Table); alongside other specified outcomes of interest including communication practices (and preventable 911 calls). Finally, the effect of the intervention on two patient outcomes (emergency department [ED] visits; 30-day readmissions; functional status) will be assessed in exploratory analyses. To determine the effect of the intervention on the **primary outcomes**, we will compare HF knowledge and HF caregiving self-

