efficacy scores by trial arm using paired t-tests for normally distributed data or Wilcoxon signed rank test for non-parametric data. We will examine the effect of randomization on the change in scores, using mixed linear regression models. Mixed-effects included a fixed effects categorical variable for time point (baseline/post-course/90 day), an indicator for study arm (control/intervention), a study arm by timepoint interaction and subject-specific random intercept. Primary analyses will be conducted using intention-to-treat, when appropriate. We will examine HHA characteristics across trial arms and adjust for covariates that are imbalanced ($p < 0.10$). We will conduct the same analyses for the secondary outcomes (burnout and job satisfaction). For patient outcomes, we will perform exploratory analyses to determine the effect of the intervention on ED visit rates and hospitalization rates; and functional status, using Poisson mixed effects regression models to account for clustering of patients within HHAs. To measure what would have occurred with usual care (e.g. without enhanced usual care or the intervention), we will assess ED visit rates and 30-day readmission rates among HHAs 90 days before vs. 90 days after randomization, adjusting for clustering of patients within HHAs, and stratified by trial arm. Analyses will be done using STATA statistical software.

Power and Sample Size: To detect minimal clinically important differences (MCID) for both outcomes (a 1-point change in mean score on the Dutch HF Knowledge Scale; an 8-point change in mean score on the HF caregiving self-efficacy), with 80% power, α at 0.05, and conservatively allowing for 15% attrition, we will need 104 HHAs (52 per arm). The overall α at 0.05 enables testing of two hypotheses using Bonferroni's method. Consistent with the goals of this study (to assess feasibility and acceptability of the intervention and obtain preliminary effectiveness estimates on primary outcomes), we have not powered our study on secondary outcomes or on patient outcomes. These calculations were done in Stata v13, College Station, TX.

Statement of the Risks/Benefits for the Study Subjects:

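### The rule for judging the two primary outcomes appears only in the power section and is never given per test; it should be written into Outcome analyses, and Holm would serve better than Bonferroni at the same overall 0.05

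*Combined protocol and SAP*

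**What the plan says.** Three places in the combined protocol and SAP bear on the threshold.

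- **Baseline analyses** (under Brief Overview of Analytic Methods) describes tests of balance between arms and closes with "All tests will be conducted at" α = 0.05. The sentence names no subset of tests.
- **Outcome analyses** lists the primary outcomes, "1) HF knowledge; 2) HF caregiving self-efficacy and" then two secondary ones. It names a paired t-test or its signed-rank counterpart, and then a model: "We will examine the effect of randomization on the change in scores, using mixed linear regression models". The model has three time points. No significance level and no multiplicity rule is given here.
- **Power and Sample Size** gives the sizing statement, "with 80% power, α at 0.05, and conservatively allowing for 15% attrition, we will need 104 HHAs (52 per arm"), and then the multiplicity rule: "The overall α at 0.05 enables testing of two hypotheses using" Bonferroni's method. It does not say whether the 0.05 used for sizing was per test or overall. The per-test value of 0.025 is not written anywhere.

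**The concern.** An analyst working from the analysis section would not find the threshold for either primary p-value. It has to be inferred from a sample-size sentence, and the one level printed in the analytic methods, 0.05, is not the one that sentence implies. If 0.05 were applied to each primary outcome, the overall 0.05 that the plan claims would not be kept. A p-value between 0.025 and 0.05 is where the outcome of the trial would turn on the reading.

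Separately, the method named is not the best available for its own purpose. With two hypotheses, Holm compares the smaller p-value with 0.025 and, if that passes, the larger with 0.05. It rejects everything that Bonferroni rejects and sometimes more, at the same familywise error. Staying with Bonferroni gives up some power for the second outcome.

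**Working it through.** **Inputs from the plan.** Two primary outcomes; overall α 0.05 with Bonferroni; 80% power; 52 per arm; 15% attrition; effects of 1 point (knowledge) and 8 points (self-efficacy).

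**Assumptions.** Two-sided tests (sidedness is not stated), a normal approximation for a two-arm comparison of means, and a correlation between the two test statistics of 0 to 0.8. The plan gives no SD.

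**1. The plan's own figure.** Without an SD, 104 cannot be reproduced forward, so I solved backward. Evaluable per arm: 52 × 0.85 = 44.2, so 44; check, 44 / 0.85 = 51.8, so 52. The detectable standardised difference is d = (z for α + z for power) × √(2/44).

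- α = 0.05: (1.960 + 0.842) × 0.2132 = 0.597, so SD = 1/0.597 = 1.67 (knowledge) and 8/0.597 = 13.4 (self-efficacy).
- α = 0.025: (2.241 + 0.842) × 0.2132 = 0.657, so SD = 1.52 and 12.2.

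Both return 52 per arm, so 104 does not reveal which α was used. Both cases are carried forward.

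**2. Power if sized at 0.05 but tested at 0.025.** Φ(2.802 − 2.241) = Φ(0.560) = 71.2% per outcome. Restoring 80% would need 2 × 3.083² / 0.597² = 53.3, so 54 evaluable, or 54 / 0.85 = 63.5, so 64 per arm (128 in total).

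**3. Familywise error.**

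- Each primary at 0.05: 1 − 0.95² = 9.75% if independent; 7.8% at correlation 0.8 (simulation).
- Each primary at 0.025: 1 − 0.975² = 4.94% if independent; never above 5%.

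**4. How often the reading matters.** The chance that a given primary p-value falls between 0.025 and 0.05 is 86.9% − 80.0% = 6.9% at the MCID if sized at 0.025, 80.0% − 71.2% = 8.8% if sized at 0.05, and 2.5% under the null.

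**5. Holm against Bonferroni, independent case by hand, sized at 0.025.** Power is 0.800 at 0.025 and 0.869 at 0.05.

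- Both, Bonferroni: 0.800² = 0.640.
- Both, Holm (both p ≤ 0.05, and not both above 0.025): 0.869² − 0.069² = 0.751.
- Per outcome, Holm: 0.800 + 0.069 × 0.800 = 0.855.
- At least one, either method: 1 − 0.2² = 0.960.

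**6. Range over correlation 0 to 0.8** (one million bivariate normal draws per setting, both effects at the MCID):

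| Sized at | Measure | Bonferroni | Holm |
|---|---|---|---|
| 0.025 | per outcome | 80% | 84–86% |
| 0.025 | both | 64–73% | 75–80% |
| 0.025 | at least one | 87–96% | 87–96% |
| 0.05 | per outcome | 71% | 76–78% |
| 0.05 | both | 51–63% | 63–71% |
| 0.05 | at least one | 80–92% | 80–92% |

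If only one effect is real, the independent-case gain on that outcome is about 0.069 × 0.025 = 0.0017 or 0.088 × 0.025 = 0.0022, that is, about 0.2 percentage points at most. With no real effect, the familywise error of Holm equals that of Bonferroni.

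**The case against.** The strongest reply is that the plan already has a rule. The 0.05 sentence ends the baseline paragraph, directly after the balance tests, and Outcome analyses begins afterwards under its own label. The only rule attached to the two hypotheses is Bonferroni. A reader might infer that a primary p-value of 0.03 is a success under one section and a failure under another. The documents do not support that: on the ordinary reading it is a failure. Nor is the 8–10% familywise error a property of the plan; it arises only if the baseline sentence is misapplied. This part of the reply stands.

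It does not close the matter. The sentence is worded without limit, and Outcome analyses acts on baseline imbalance at p < 0.10, so 0.05 is not the working baseline rule either. That weakens the baseline-only reading without excluding it. On either reading, the outcome text lacks a threshold.

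The reply on Holm is that Bonferroni is a legitimate prespecified choice, that writing 0.025 would remove the ambiguity by itself, and that Bonferroni comes with simple matching 97.5% intervals while Holm does not. The last point has weight in a pilot that seeks preliminary effect estimates. All of this is true. It makes Holm an inexpensive improvement, not the correction of an error.

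Finally, no threshold gives one verdict per outcome until the deciding test is fixed. Outcome analyses offers both a paired test and a mixed model, with post-course and 90-day follow-up.

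**Conclusion.** The point holds as a gap in wording plus a cheap gain in power. The implied 0.025 is unwritten, the outcome analyses are silent, and one unrestricted sentence invites misreading. Bonferroni is valid, but for testing it is dominated by Holm.

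The gain is confined to the second hypothesis. It is about 4 to 6 percentage points per outcome and 7 to 13 points for winning both. It requires both effects to be real at the MCID, and its level depends on whether the sizing α was 0.025 or 0.05, which the plan does not say. The SDs, two-sidedness and correlations used here are assumptions.

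A reader might conclude that the trial has no valid error control, or that this must be corrected before the trial can be interpreted. Neither follows, because the Bonferroni rule in Power and Sample Size already holds overall error to 5%. Severity is low to moderate.

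**What to change.** - In Outcome analyses, name one primary between-arm contrast (test and time point) for each of HF knowledge and self-efficacy. State that the two p-values are judged by Holm at an overall two-sided 0.05: the smaller against 0.025 and, only if it passes, the larger against 0.05.
- Limit the 0.05 sentence in Baseline analyses to baseline tests.
- In Power and Sample Size, name the same rule, and state the per-test α and the SDs behind 104.
- Leave intention to leave and job satisfaction labelled as secondary; the change does not require calling them exploratory.

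The cost is a few sentences and no extra participants. There are two conditions. First, Holm has no simple matching simultaneous intervals, so the plan should say which intervals will be reported. Second, Holm relaxes the threshold for the second outcome, so it must be adopted before anyone has seen results by arm. The document is dated 4/22/2025, its invitation script gives an event on 1/24/23, and the study period is 24 months, so data may already exist; the documents do not say. If arm-level results have been seen, keep Bonferroni and write 0.025 per primary outcome into Outcome analyses.

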Title of the Project: Leveraging Home Health Aides to Improve Patient Outcomes in Heart Failure: A Pilot Randomized Controlled Trial

NCT #: NCT04239911

Document Date: 4/22/2025

Study Title: Leveraging Home Health Aides to Improve Outcomes in Heart Failure: Pilot Randomized Controlled Trial

Principal Investigator: [name], MPH, MS

Funder: National Heart, Lung, and Blood Institute (K23HL15060)

VNS HEALTH – Research Protocol

Background: Heart failure (HF) affects 6 million people in the U.S. and costs over 30 billion dollars per year. There are 1 million HF hospitalizations per year, and 25% of Medicare beneficiaries admitted for HF are readmitted within 30 days. Previous interventions to reduce HF readmissions have had mixed results, perhaps in part because they did not involve home health aides (HHAs). After a HF hospitalization, a third of Medicare beneficiaries are discharged home with home care services, which may include support from HHAs. Unlike physicians or visiting nurses, HHAs are with patients on a near-daily basis, sometimes up to 24 hours per day. However, my prior qualitative research suggests that HHAs do not receive HF-specific education and are not confident caring for HF patients. In addition, my prior work has shown that HHAs experience difficulty reaching their supervising nurses (at their home care agencies) when they have questions or need help managing patients in the home. As a result, HHAs often resort to calling 9-1-1 and subsequently bringing their patients to the emergency department (ED). While some ED visits may be clinically appropriate, many may be avoidable. Interventions that can optimize and improve the experience of HHAs caring for the HF patients have the potential to improve HHAs own self-efficacy but also patient outcomes.

To that end, we have developed a HF intervention for HHAs comprised of a) remote classroom education on HF and b) an mHealth app containing HF educational content and a messaging application that connects HHAs and their nurse supervisors. This intervention requires feasibility testing, as well as preliminary testing of its acceptability and effectiveness among HHAs.

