Study Purpose and Specific Aims: To conduct a pilot randomized controlled trial (RCT) of the intervention among HHAs caring for adults admitted to home care with a primary diagnosis of HF, to determine its feasibility and its effect on HHAs (HF knowledge and caregiving self-efficacy), and to explore its effect on HF patient outcomes (ED visits and 30-day readmissions). If successful, the result of this project will be a novel and scalable intervention that has the potential to improve HHAs' ability to care for HF patients and reduce ED visits and 30-day readmissions.

[figure not shown]
Study Design: PI [name] will design and conduct a 2-arm pilot RCT in partnership with the VNS Health's licensed home care agency (Partner's in Care) under the guidance of [name] (VNS Health-Site PI) and [name], MSW(VNS Health-Co-I) and leaders at Partners in Care. [name] ([name] mentor at Weill Cornell Medicine, expert in pragmatic clinical trials), [name] ([name] at Weill Cornell, expert in care coordination, including measuring the effectiveness of interventions designed to improve care coordination) will guide her throughout the study. In addition, [name] (adviser in health technology) will advise her. Over a two-year period, 104 HHAs will be enrolled in the pilot and 52 will be randomly assigned to the enhanced usual care arm (HF training course alone) and 52 to the intervention arm (HF training course *plus* mHealth app [Partner's in Care's Care Connect

app with new features]). Four nurses will also be recruited to participate in the pilot. Because withholding education from the control arm is not favorable to HHAs and since educational interventions alone are unlikely to affect outcomes, we will not have a usual care arm. Each HHA will be followed for 90 days, since this post-discharge period is clinically challenging, and it aligns with policies that reward or penalize hospitals and agencies based on readmissions. A VNS Health staff member will help coordinate the trial and attend team meetings, assuring that the agency's priorities are integrated. The study will occur in a 24-month period.

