An overview of the pilot RCT and the randomization scheme is shown in the Figure below. After being consented, all HHAs will attend a virtual orientation session and virtual HF training course. Prior to the course, all HHAs will complete a baseline questionnaire (see attached survey document) and be randomized in a 1:1 ratio (T1). The training course will be conducted via Zoom and led by WCM investigators and VNS Health staff members. After taking the course, HHAs in both arms will take a short post-course questionnaire (to assess the two primary outcomes; knowledge and HF caregiving self-efficacy). HHAs randomized to the enhanced usual care arm will receive a just-in-time course refresher via their Care Connect app (self-driven educational content) prior to caring for their HF patient. HHAs randomized to the intervention will receive a just-in-time course refresher as well as an app training session from a Weill Cornell Medicine research assistant (overseen by [name] in computer science). HHAs in this arm will be encouraged to use the app when they have questions about their patient, want to access HF-related content, or need to communicate with the nurse. To reinforce their use of the use of the application chat features, they will receive "do not reply" text based notifications reminding them that the feature is there and can be used. Following the care of their first patient, HHAs in both arms will take a follow-up questionnaire. Each HHA will be involved in the study for 90 days. During that time, if the HHA is assigned to a new HF patient, they can continue participation although they will remain randomized to their original treatment arm to avoid contamination. De-identified data on HF patients cared for by the HHAs (demographics, clinical conditions, ED visits; 30-day/90-day readmissions; hospitalization; functional status; and quality of life) will be retrospectively collected by the VNS Health from intake/referral data and OASIS. HHAs will receive \$100 for participating; they will receive \$25 at trial start, \$25 following the completion of the heart failure training course and survey 2, \$25 following the 45-day (mid-study) interview, and \$25 following the final survey.

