At the start of the trial, during the kickoff session, nurses will be introduced to the study and thoroughly informed of the study details. After this time, nurses will provide verbal informed consent to the study team. The study team feels that this is the most efficient use of their time; it is also more feasible since we do not plan to collect additional data from nurses (demographics, outcomes, etc.). As such, it was felt there would not be a need to build a separate e-consent project in REDCap for the electronic consent of nurses, nor will this be feasible within our allocated staff time. Nurses in the trial will respond to alerts and messages from HHAs using the app. Nurses will also receive an orientation to the Care Connect messaging features prior to the start of the trial from the WCM/Cornell Tech team. At the end of the trial, nurses will receive \$100 for participating.

Figure . Randomization and Data Collection for RCT

Evaluation and Outcome Measures: There are three main outcomes for this study:

- 1) *Feasibility*
- 2) *Acceptability*
- 3) *Effectiveness*

To assess feasibility we will assess: the reach of the intervention by tracking the number of HHAs approached and enrolled; the effectiveness through baseline and follow-up assessments; the adoption by the number of HHAs who completed the training course (both arms), participated in app orientation session (intervention arm), and completed the trial (both arms); the implementation through intervention fidelity (mHealth app usage, educational content accessed [both arms], Care Connect messaging with nurses [intervention arm], underlying reasons for Care Connect messaging between HHAs and nurses [intervention arm]). This feasibility data will be extracted from the mHealth app by the Care Connect team (lead, [name]) and [name]. *Acceptability* will be assessed with exit interviews with HHAs, nurses, and agency staff from both trial arms. Additional exit interviews will be conducted with a subset of patients from both trial arms. *Effectiveness* will be assessed for *two primary outcomes*: 1) HF knowledge; 2) HF caregiving self-efficacy and *two secondary outcomes*: 1) job satisfaction and 2) intention to leave (See Table). Patient outcomes (ED visits; 30-day/90-day readmissions; hospitalization; functional status; and quality of life) will be assessed in exploratory analyses (See Table 1).

Table 1. Effectiveness Outcome Measures for Pilot RCT

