Outcomes	Validated Scale	Description	Data source
Primary Outcomes (HCWs)			
HF knowledge	Dutch HF Knowledge Scale	15 item scale measures HF knowledge in general, knowledge of HF treatments, and HF symptom recognition. Scores range from 0-15, with higher scores indicating higher HF knowledge.	Baseline and follow-up questionnaires
HF caregiving self-efficacy	Caregiver Contribution to Self-Care in HF Index (CC-SCHFI)	22-item scale measures caregivers' 1) contributions to HF maintenance; 2) contributions to HF management; and 3) HF caregiving self-efficacy (confidence). Each of these 3 subscales are scored independently. The third sub-scale (self-efficacy) will be the main outcome. Self-efficacy scores range from 0-100, with higher scores indicating greater self-efficacy.	Baseline and follow-up questionnaires
Secondary Outcomes (HCWs)			
Intention to Leave	Turnover intention scale	2-item scale measures workers' intentions of 1) leaving their current job (at their agency) and 2) searching for a new job (in another field) in the next year	Baseline and follow-up questionnaires
Job satisfaction	Work Domain Satisfaction Scale	This 5-item scale measures 1) job satisfaction among care workers; and 2) examines the associations with work environment factors, work stressors, and health issues. Scores range from 5-20, with higher scores indicating stronger satisfaction.	Baseline and follow-up questionnaires
Other Specified Outcomes			
Communication practices	Preventable 911 Calls	2 novel questions “I have called 911 when that could have been prevented if I had been able to reach my supervisor/the nurse.” And “I have called 911 when that could have been prevented if my supervisor and I had been able to reach the client's doctor.”	Baseline and follow-up questionnaires

		Responses for both included a 7-point likert scale of: very strongly disagree, strongly disagree, disagree neutral, agree, strongly agree, very strongly agree. Both questions dichotomized into “agree”, “strongly agree”, and “very strongly” vs. all other responses.	
Patient Outcomes (exploratory)			
30-day readmission; 90-day (all-cause)	N/A	A readmission to any hospital (for any reason) at 30-days after start of home care episode.	Follow-Up VNS Health administrative data
Emergency department visit (all-cause)	N/A	A visit to the emergency department of any hospital (for any reason) after start of home care episode	Follow-Up VNS Health administrative data

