The HHAs will receive a HF training course and will perform routine caregiving tasks while caring for HF patients in this study. Those in the intervention arm, will also have the opportunity to engage (electronically) with their supervisors to ask clinical questions, rather than usual care (trying to reach them by phone). The questions will be asked via a secure, HIPAA protected function on the mHealth app (Care Connected) (monitored by [name], adviser in health technology, and the Care Connect team) and no identifying information will be used. All participants will be asked to complete questionnaires at 4 time points during the trial, which contain no identifying information. Although every reasonable effort has been taken, confidentiality during Internet communication procedures cannot be guaranteed and it is possible that additional information beyond that collected for research purposes may be captured and used by others not associated with this study. The VNS Health and Weill Cornell Medicine take the privacy and security of study data seriously. To preserve confidentiality, data will be collected and stored at Weill Cornell Medicine on secure servers monitored by Weill Cornell Medicine ITS. Data will only be available to authorized individuals on the study team. When necessary, data will be sent over private connections secured by the WCM ITS. Furthermore, data sets will be encrypted and reported in aggregate form only. VNS Health study staff will have initial access to patient-level data in order to merge data sources and identify the patient cohort of interest; and to link a home health aide to a specific patient for intervention workflow processes. The outcome file that will be shared with Weill Cornell study staff will include a Study ID, the age of the patient, and information on hospitalizations and ED visits within 90 days of the start of the intervention. Both VNS Health and Weill Cornell study staff will have access to the communication (via the Chat feature in Care Connect) between the home health aide and the supervisory nurses. It is possible that patient name and other identifiers will be included within this communication. At both sites all data will be secured in password protected, HIPAA secured data systems. Sharing of data across sites will be done through the VNS Health approved email encryption process and/or through the approved MSTEams application. For the entire study, data will be reported in aggregate form only. PI [name] will ensure that all study team members will be trained thoroughly in the need to maintain confidentiality and no information collected will be used for any purpose other than those stated in the informed consent form. Rules for handling confidential data and security of patient information will be strictly abided by all study team members in charge of handling data.

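### The patient data include neither death nor the end of home care, and the Poisson models state no exposure time, so the exploratory ED and readmission comparisons could mislead if either differs by arm

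*Combined protocol and SAP*

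**What the plan says.** The aim for patients, under Study Purpose and Specific Aims, is "to explore its effect on HF patient outcomes (ED visits and 30-day readmissions" (closing bracket omitted). Study Design lists the retrospective patient data as "demographics, clinical conditions, ED visits; 30-day/90-day readmissions; hospitalization; functional status; and quality of life". Evaluation and Outcome Measures states: "Patient outcomes (ED visits; 30-day/90-day readmissions; hospitalization; functional status; and quality of life) will be assessed in exploratory analyses".

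Table 1 defines 30-day readmission as "A readmission to any hospital (for any reason) at 30-days after start of home care episode" and the ED outcome as "A visit to the emergency department of any hospital (for any reason) after start of home care episode". Hospitalization is any admission during the study period.

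Data to be Collected and Analyzed has the VNS Health programmer extract ED visits, 30-day readmissions and functional status from agency clinical records and administrative data. OASIS data are analysed at VNS Health. Under Brief Overview of Analytic Methods, exploratory analyses are "to determine the effect of the intervention on ED visit rates and hospitalization rates", and on functional status, with Poisson mixed models that account for clustering of patients within HHAs. ED visit and 30-day readmission rates are also compared for the 90 days before and after randomization, by arm.

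The section on privacy and confidentiality says that the outcome file shared with Weill Cornell "will include a Study ID, the age of the patient, and information on hospitalizations and ED visits within 90 days".

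**The concern.** The arms differ mainly in access to nurse messaging. The Background explains that HHAs who cannot reach a nurse often call 911, and it grants that "While some ED visits may be clinically appropriate, many may be avoidable". A fall in ED visits can therefore be read in more than one way, and the reader needs to see whether patients were alive and under observation while no visit was recorded.

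Death is a competing event for both ED visits and readmission, and the end of home care may end the agency's sight of the patient. If neither is recorded, a rate can fall because fewer patients were at risk. The other patient measures do not fill the gap: functional status and the KCCQ-12 can be obtained only from survivors, and the patient interviews cover a subset approached at 90 days.

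At stake is the interpretation of the exploratory ED, hospitalization and readmission results, which a later trial might build on. HHA knowledge and self-efficacy are not touched.

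**Working it through.** **1. What each place contains**

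| Place | Patient events named | Death | End of home care | Time at risk or censoring |
|---|---|---|---|---|
| Specific Aims | ED visits, 30-day readmission | no | no | no |
| Study Design | ED visits, 30/90-day readmission, hospitalization, function, quality of life | no | no | no |
| Evaluation and Outcome Measures | same five | no | no | no |
| Table 1 | same five | no | no | start of home care for readmission and ED visit; no rule for death or exit |
| Data to be Collected and Analyzed | ED visits, 30-day readmission, function | no | no | no |
| Brief Overview of Analytic Methods | ED visits, hospitalization, 30-day readmission, function | no | no | clustering only |
| Shared outcome file | hospitalizations, ED visits within 90 days | no | no | no |

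**2. What the definitions imply by default.** Take a patient who dies at home on day 12 with no earlier event. No readmission by day 30 and no ED visit exists, so both outcomes are zero. A patient who leaves home care on day 20 with no earlier event is also zero, unless the agency sees later events. The plan does not say whether it does.

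**3. Inputs for size.** The plan has no mortality or exit figure, so there is nothing of its own to reproduce. Two numbers come from it: 52 HHAs per arm (Power and Sample Size) and a 25% 30-day readmission rate among Medicare beneficiaries admitted for HF (Background). The rest are assumptions: one HF patient per HHA, 5% to 15% dying within 90 days, and 20% to 50% of those dying without an ED visit or admission.

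**4. Patients dead but event-free, per arm**
- Low: 52 × 0.05 × 0.20 = 0.5
- High: 52 × 0.15 × 0.50 = 3.9

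This is a level within one arm, not a difference between arms. If three such deaths in one arm each replaced an event and none occurred in the other, that arm's event proportion would fall by 3/52 = 5.8 percentage points.

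**5. Count model with no exposure term, same true event rate in both arms.** Let d be the proportion dying in an arm and f the share of the 90 days lost per death. Then

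apparent rate ratio = (1 − d_int × f) / (1 − d_ctl × f).

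| Deaths, control vs intervention | f = 0.25 | f = 0.50 | f = 0.75 |
|---|---|---|---|
| 5% vs 5% | 1.000 | 1.000 | 1.000 |
| 5% vs 10% | 0.987 | 0.974 | 0.961 |
| 5% vs 15% | 0.975 | 0.949 | 0.922 |

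Example: (1 − 0.15 × 0.75) / (1 − 0.05 × 0.75) = 0.8875 / 0.9625 = 0.922. The formula also serves for early exit, with d the proportion leaving, if events after exit go unseen.

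**6. Deaths that replace readmissions in one arm.** With true risk 0.25 and a proportion x dying at home instead of being readmitted, apparent risk ratio = (0.25 − x) / 0.25.

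| x | Readmission alone | Readmission or death |
|---|---|---|
| 0.01 | 0.96 | 1.00 |
| 0.02 | 0.92 | 1.00 |
| 0.05 | 0.80 | 1.00 |
| 0.10 | 0.60 | 1.00 |

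The composite stays at (0.25 − x + x) / 0.25 = 1.00, so it exposes the substitution that readmission alone hides.

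**The case against.** A reader might infer that the analyst is bound to score a death as event-free with full follow-up. The documents do not say so. They are silent, and Poisson models for rates routinely take an exposure term, which the plan neither states nor excludes. What stands is that zero events is the default under Table 1 when nothing else is written.

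The shared file is limited evidence by itself. Its description sits in the privacy section and need not be exhaustive. It also names no trial arm and no HHA identifier, both needed for the planned models, so it is hardly the whole analysis dataset. VNS Health holds patient-level data and could censor or exclude patients from its own records. This is fair, but an unwritten capability is not a plan, and the extraction and outcome lists have the same gap.

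A second tempting inference is that messaging delays emergency care and that the delay would look like benefit. Nothing in the documents shows such a delay. Messaging is set against phoning the nurse and waiting on hold, and delayed care that ends in an ED visit or admission is still counted. False benefit needs losses that differ by arm or replace events in one arm.

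The plan also has related process measures: two items on preventable 911 calls, reasons for messaging, and access to the chats. These help interpretation but do not give vital status.

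Finally, the patient outcomes are exploratory and unpowered, and deaths will be too few to test. That limits the severity. It does not remove the case for recording them.

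**Conclusion.** The omission is certain: death and the end of home care appear in no patient outcome list, extraction sentence or analysis sentence, and no exposure time is stated. The consequence is conditional. If deaths or exits are unequal, or replace ED visits or readmissions in one arm, the comparison is distorted in favour of the arm with more of them. If deaths are equal in number and timing, no spurious difference arises.

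The size rests wholly on assumed mortality. Lost person-time alone has a modest effect: at most about 8% on the rate ratio in the scenarios shown (0.922). Substitution in one arm can do more: a risk ratio of 0.80 if 5 percentage points of patients die instead of being readmitted. Both calculations place the excess deaths in the intervention arm only to show direction; the documents give no reason to expect that.

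Severity is minor to moderate. The HHA primary outcomes and the sample size are unaffected.

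**What to change.** - Add all-cause death within 30 and 90 days of the start of home care to the exploratory patient outcomes in Table 1.
- Add vital status, date of death and date home care ended, as study days, to the VNS Health extraction and to the shared outcome file.
- Use time alive and under home care as the exposure in the Poisson models for ED visit and hospitalization rates.
- For 30-day and 90-day readmission, report readmission-or-death beside readmission, since an exposure term does not directly serve a yes/no outcome.
- Show deaths by arm, descriptively, next to the ED and readmission results.

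The cost is a few fields in an extraction already planned from agency records, plus one descriptive table. It changes no intervention, visit or sample size. The downside is that deaths after home care ends may be incompletely known to the agency, and counts will be too small to test, so the report should state both limits.
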